3.3.2 Investigational Product Administration

In the Blinded Part A of the study, investigational product will be administered as an IM injection into the deltoid muscle on a 2-dose injection schedule on Day 1 and Day 29, with a 28-day interval between doses. Each injection will have a volume of 0.5 mL and contain mRNA-1273 50 µg, mRNA-1273 100 µg, or saline placebo. Preferably, vaccine should be administered into the nondominant arm.

In the open-label Part B of the study, mRNA-1273 vaccine will be administered as an IM injection into the deltoid muscle following the injection schedule for each group based on the product received: participants who received 1 or 2 doses of mRNA-1273 (50 µg and 100 µg) will receive a single booster dose of mRNA-1273 50 µg on OL-Day 1 in Part B ([Table 11](#)); participants who received placebo in Part A will receive 2 doses of mRNA-1273 100 µg on open-label (OL)-Day 1 and OL-Day 29 of Part B ([Table 11](#)). In addition, participants who received only 1 dose of mRNA-1273 (50 µg or 100 µg) in Part A, will be receive a single booster dose of mRNA-1273 (50µg) on OL-D1 in Part B ([Table 12](#)).

In the open-label Part C of the study, the investigational product will be administered as a single IM injection into the deltoid muscle on the day of the participant's consent (OL-D1). Each injection will have variable dose volumes; the 20-µg dose of mRNA-1273.351 is 0.2 mL, the 50-µg dose of mRNA-1273.351 is 0.5 mL, and the 50-µg dose of pharmacy prepared mixture of mRNA-1273/mRNA-1273.351 is 0.5 mL.

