- Daily oral body temperature measurement should be performed at approximately the same time each day using the thermometer provided by the study site. If body temperature is taken more than once in a given day, only the highest temperature reading should be recorded.
- Measurement, as applicable, for solicited local ARs (injection site erythema and swelling/induration); the size measurements will be performed using the ruler provided by the study site.
- Participants will be queried by the eDiary whether any medications were taken to treat or prevent pain or fever on a day of injection or for the 6 subsequent days.

The eDiary will be the only source documents allowed for solicited systemic or local ARs (including body temperature measurements). Participants will be instructed to complete eDiary entries daily. The participant will have a limited window on the following day to complete assessments for the previous day; quantitative temperature recordings and measurement of any injection site erythema or swelling/induration reported on the following day may be excluded from the analyses of solicited ARs.

Any new safety information reported during safety telephone calls or at site visits (including a solicited reaction) that is not already captured in the eDiary will be described in the source documents as a verbally reported event. Any AR reported in this manner must be described as an unsolicited event and therefore entered on the AE eCRF.

Study site staff will review eDiary data with participants at the Day 8 and Day 36 visits in the blinded Part A of the study. In the open-label Part B of the study, eDiary data will be reviewed in person on open-label (OL) Day 8 for participants receiving a single booster ([Table 12](#)) and via phone call 7 days after each vaccination for those participants receiving 2 doses of 100 µg mRNA-1273 ([Table 11](#)). In Part C of the study, eDiary data will be reviewed in person on open-label Day 8 ([Table 12](#)).

The eDiary will also be used after the Day 57 visit (including OL-Day 57 in Part B and Part C) to capture the occurrence of AEs, MAAEs, SAEs, or AEs leading to study withdrawal, every 4 weeks from Day 71 through Day 183 in Part A ([Table 9](#)), from OL-Day 71 through OL- Day 155 in Part B ([Table 11](#) and [Table 12](#)) and Part C ([Table 12](#)), and from Day 223 through Day 363 in Part A only ([Table 9](#)).

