4.3.2 Part B, Open Label

4.3.2.1 Primary Endpoints (Part B, Open Label)

4.3.2.1.1 Primary Safety Endpoints

The primary safety objective will be evaluated by the following safety endpoints:

- Solicited local and systemic ARs through 7 days after each injection.
- Unsolicited AEs through 28 days after each injection.
- MAAEs through the entire study period.
- SAEs throughout the entire study period.
- Vital sign measurements and physical examination findings.

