4.6.2 Safety Analyses

Safety and reactogenicity will be assessed by clinical review of all relevant parameters including solicited ARs (local and systemic events), unsolicited AEs, SAEs, MAAEs, AEs leading to discontinuation, safety laboratory test results (Part A only), vital signs, and physical examination findings.

Solicited ARs and unsolicited AEs will be coded by system organ class and preferred term according to the MedDRA for adverse reaction terminology. The Toxicity Grading Scale for Healthy Adult and Adolescent Volunteers Enrolled in Preventive Vaccine Clinical Trials ([DHHS 2007](#)) is used in this study with modification for rash, solicited ARs, and vital signs ([Table 6](#)).

Rash will be graded as:

- Grade 0 = no rash
- Grade 1 = localized without associated symptoms
- Grade 2 = maculopapular rash covering < 50% body surface area
- Grade 3 = urticarial rash covering > 50% body surface area
- Grade 4 = generalized exfoliative, ulcerative, or bullous dermatitis

All safety analyses will be based on the Safety Set, except summaries of solicited ARs which will be based on the Solicited Safety Set. All safety analyses will be provided by age cohort (for Part A and Part B) unless otherwise specified.

The number and percentage of participants with any solicited local AR, with any solicited systemic AR, and with any solicited AR during the 7-day follow-up period after each injection will be summarized. A 2-sided 95% exact CI using the Clopper-Pearson method will be provided for the percentage of participants with any solicited AR.

Number and percentage of participants with unsolicited AEs, SAEs, MAAEs, Grade 3 or higher AEs, and AEs leading to discontinuation from study vaccine or participation in the study will be summarized.

Number of events of solicited ARs, unsolicited AEs/SAEs, and MAAEs will be reported in summarization tables accordingly.

For all other safety parameters, descriptive summary statistics will be provided. [Table 8](#) summarizes the analysis strategy for safety parameters.

Table 8: Analysis Strategy for Safety Parameters

Safety Endpoint	Number and Percentage of Participants, Number of Events	95% CI
Any Solicited AR (overall and by local, systemic)	X	X
Any Unsolicited AE	X	
Any SAE	X	
Any Unsolicited MAAE	X	
Any Unsolicited Treatment-Related AE	X	
Any Treatment-Related SAE	X	
Discontinuation due to AE	X	
Any Grade 3 and above AE	X	
Any Treatment-Related Grade 3 and above AE	X	

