5.2. Solicited Safety Set

Solicited Safety Set (Part A, Blinded Phase)

The Solicited Safety Set for Part A consists of all participants who are randomized and received any study injection during Part A, and contribute any solicited AR data, ie, have at least one post-baseline solicited safety assessment in Part A. The Solicited Safety Set will be used for the analyses of solicited ARs and subjects will be included in the vaccination group corresponding to the study injection they actually received during Part A. In addition, the following Solicited Safety Set is defined for each injection separately.

The First (Second) Injection Solicited Safety Set for Part A consists of all subjects in the Solicited Safety Set (Part A) who have received the first (second) study injection during Part A and have contributed any solicited AR data from the time of first (second) study injection through the following 6 days.

Subjects will be analyzed according to the vaccination group a subject received during Part A, rather than the vaccination group to which the subject was randomized. Subjects who receive a second injection that is different from the first injection will be summarized under the higher dose of vaccination group (eg, Placebo < mRNA-1273 50 µg < mRNA-1273 100 µg).

Solicited Safety Set (Part B, Open-Label Phase)

The Solicited Safety Set for Part B consists of all participants who are randomized in Part A and received any study injection during Part B, and contribute any solicited AR data, ie, have at least one post-baseline solicited safety assessment in Part B. The Solicited Safety Set will be used for the analyses of solicited ARs and subjects will be included in the vaccination group corresponding to the study injection they actually received in Part B, 100 µg of mRNA-1273 as 2 doses injection (for participants who received placebo injection in Part A) vs booster dose.

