All solicited ARs analyses will be based on the Solicited Safety Set. All solicited ARs analyses will be provided by age cohort and vaccination group as defined in [Section 6.1](#) for each injection (first or second) (Part A only) and any injection (Part A and Part B separately), unless otherwise specified.

The number and percentage of subjects who reported each individual solicited local AR (has a severity grade of Grade 1 or greater) and solicited systemic AR (has a severity grade of Grade 1 or greater) during the 7-day follow-up period after each injection will be tabulated by age cohort, vaccination group, severity grade, and injection. The number and percentage of subjects who reported each individual solicited AR will also be summarized by age cohort, vaccination group, severity grade, day of reporting and injection. The number and percentage of subjects experiencing fever (a temperature greater than or equal to 38.0°C/100.4°F by the oral, axillary, or tympanic route) by severity grade will be provided.

A two-sided 95% exact confidence interval (CI) using the Clopper-Pearson method will be provided for the percentage of subjects who reported any solicited local AR, solicited systemic AR, or any solicited AR.

The onset of individual solicited AR is defined as the time point after each injection at which the respective solicited AR first occurred. The number and percentage of subjects with onset of individual solicited AR will be summary by age cohort, vaccination group, study day relative to the corresponding injection (Day 1 through Day 7), and injection.

The number of days reporting each solicited AR will be summarized descriptively and for the following time windows (1-2 days, 3-4 days, 5-6 days, and ≥ 7 days) by age cohort, vaccination group, and injection. The number of days will be calculated as the days of the solicited AR is reported within the 7 days of injection including the day of injection, no matter it is intermittent or continued. If the solicited AR continues beyond 7 days, the consecutive days a solicited AR is reported after 7 days will be included (eg, an event that lasted 5 days in the first 7 days post injection and 3 consecutive days beyond 7 days post injection, the duration will be reported as 8 (5+3) days.)

The number and percentage of subjects who reported solicited rash and lymphadenopathy assessed by healthcare provider will be summarized by age cohort, vaccination group, severity grade, and injection.

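### SAP 6.3.2.1 confines by-injection reactogenicity summaries to Part A, then tabulates by injection without naming a Part, so per-dose results for the two-dose Part B crossover group are not secured

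*SAP*

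**What the plan says.** Protocol 4.3.2.1.1 lists, as a Part B primary safety endpoint, "Solicited local and systemic ARs through 7 days after each injection". Section 3.4.1 of the SAP for Parts A and B repeats it. Protocol 4.6.2 plans that the number and percentage of participants "with any solicited AR during the 7-day follow-up period after each injection will be summarized", with no restriction to Part A.

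Part B includes a two-dose group. Under protocol 3.3.2, "participants who received placebo in Part A will receive 2 doses of mRNA-1273" at 100 µg, on OL-Day 1 and OL-Day 29. Protocol Table 11 activates the eDiary at both doses, and protocol 3.4.2 has the diary reviewed "via phone call 7 days after each vaccination for those participants receiving 2 doses".

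SAP 6.3.2.1 opens its analysis rules with a sentence covering all solicited reaction analyses. These are to be given "for each injection (first or second) (Part A only) and any injection (Part A and Part B separately"), unless the SAP specifies otherwise. SAP 5.2 follows the same line: "The First (Second) Injection Solicited Safety Set for Part A consists of all subjects in the Solicited Safety Set (Part A"). For Part B it defines one set, made up of randomized participants who "received any study injection during Part B, and contribute any solicited AR data".

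**The concern.** The parenthesis limiting by-injection analyses to Part A has no evident purpose except to leave Part B out of them. If programmers follow it, the Placebo - mRNA-1273 group gets one figure per reaction, covering two doses four weeks apart.

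The split matters because the protocol expects the doses to differ. Its Phase 1 summary (section 1.3) reports that incidence and severity generally increased after the second injection. A combined rate cannot show whether that recurs in the crossover group. It also cannot be set beside the Part A 100 µg arm dose by dose, although that arm has the same dose and interval and is reported by injection.

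The restriction is also undeclared. SAP Section 1 says the SAP prevails where its methods differ from the protocol, and the list of changes in SAP Section 7 does not include this one.

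**Working it through.** **1. The texts side by side**

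| Place | Part B, by injection? |
|---|---|
| Protocol 4.3.2.1.1 and SAP 3.4.1 (endpoint) | Each injection |
| Protocol 4.6.2 (method) | Each injection, no Part excluded |
| SAP 6.3.2.1, governing sentence | Any injection only, exceptions allowed |
| SAP 6.3.2.1, five later tabulations (individual reactions by grade; by day of reporting; onset; number of days; rash and lymphadenopathy) | By injection, no Part named |
| SAP 6.3.2.1, exact confidence interval for any local, any systemic or any reaction | Injection not mentioned |
| SAP 5.2 (analysis sets) | Per-injection sets for Part A only |
| SAP 6.2.4 (eDiary medication summaries) | First, second and any injection, for Part A and Part B |

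The five later tabulations could be read as exceptions to the governing sentence, or as applying only where that sentence allows. Nothing settles which. Even on the first reading, the headline percentages with confidence intervals are not restored for Part B by dose. Under SAP 6.2.4 as written, pain and fever medication would be split by dose in Part B while the reactions themselves might not be.

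**2. Size of the group.** Protocol 1.3 reports 200 placebo participants with a first Part A injection and 194 with a second. The ceiling is therefore about 200. The documents do not state Part B uptake.

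**3. What an any-injection rate can show.** Let p1 and p2 be the rates after each dose and p12 the proportion reacting to both. Then

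any = p1 + p2 − p12, so max(p1, p2) ≤ any ≤ min(1, p1 + p2).

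Under independence, any = 1 − (1 − p1)(1 − p2). The rates below are assumed, because the documents give none for this group.

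| p1 | p2 | Lowest | If independent | Highest |
|---|---|---|---|---|
| 20% | 60% | 60% | 1 − 0.8 × 0.4 = 68% | 80% |
| 60% | 60% | 60% | 1 − 0.4 × 0.4 = 84% | 100% |

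An observed 60% fits a threefold rise from dose 1 to dose 2 (20% then 60%) and no rise at all (60% then 60%), each with complete overlap of reactors. This holds whatever the dependence between doses.

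**4. The denominator for dose 2.** Without a per-injection set, the default in SAP 6.1 applies: everyone in that age cohort and vaccination group within the analysis set. That counts people who missed dose 2. If Part B repeated the Part A placebo pattern (assumed), 116 reactors would be 116/194 = 59.8% of those dosed but 116/200 = 58.0% by default. The dilution factor is 194/200 = 0.97, which is small but avoidable.

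**5. Whether per-dose reporting is worthwhile.** Clopper-Pearson 95% intervals for a single dose:

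| Observed | n = 200 (ceiling) | n = 100 (assumed uptake) |
|---|---|---|
| 10% | 6.2–15.0% | 4.9–17.6% |
| 30% | 23.7–36.9% | 21.2–40.0% |
| 60% | 52.9–66.8% | 49.7–69.7% |

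These are usable descriptive estimates.

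**6. The plan's own figures.** SAP Table 2 reproduces. For n = 100, 200 and 400, the upper limits with one event are 5.446, 2.754 and 1.385% (stated 5.45, 2.75 and 1.38). The lowest detectable rates, 1 − 0.05^(1/n), are 2.951, 1.487 and 0.746% (stated 2.95, 1.49 and 0.75). Nothing here depends on them.

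**The case against.** The strongest reply is that this is a drafting slip. The governing sentence allows exceptions, five later tabulations use injection as a factor without limiting it to Part A, and SAP 6.2.4 splits Part B by dose. The table shells that SAP 6.1 mentions are not in the documents and may already show the split. This stands as far as it goes. A reader might infer that Part B will certainly be reported only for any injection, or that a primary endpoint will go unreported; the text does not support so firm a claim. The endpoint wording can also be read as an observation window, which an any-injection summary respects. Protocol 4.6.2 is harder to read that way.

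Three other inferences go too far:

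- **That no denominator exists for a Part B dose.** SAP 6.1 supplies a default; it is imprecise for dose 2.
- **That comparison with Part A is blocked.** Any-injection results are planned for both Parts. Only the by-dose comparison is lost, and the plan does not call for a formal one.
- **That the combined figure must differ from both per-dose rates.** That needs an assumption such as independence. If everyone who reacted to dose 1 also reacted to dose 2, it would equal the dose 2 rate. The table would still not reveal this.

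It is also fair to say that Part A describes the two-dose 100 µg pattern by injection in about 200 randomized recipients, that individual reactions are listed, and that the study tests no hypotheses. These points limit the consequence but do not reconcile the text.

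**Conclusion.** The point holds as an internal inconsistency whose plain reading narrows a Part B primary safety summary without saying so. SAP 6.3.2.1 and SAP 5.2 together point to any-injection reporting for Part B, while the endpoint, protocol 4.6.2 and the later by-injection tabulations point the other way.

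The reach is limited to the two-dose Placebo - mRNA-1273 group, at most about 200 people. For booster recipients, who receive one Part B injection, any and each are the same. No data are lost and no inference or decision rule is affected. What would be lost is the rate after each dose in that group and the by-dose comparison with the Part A 100 µg arm.

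The conclusion that a combined rate cannot recover the per-dose rates rests only on the bounds and needs no assumption about dependence. The illustrative rates, the uptake of 100 and the 194-of-200 second-dose pattern in Part B are assumptions. The text should be corrected before the final Part B analysis; it is not a threat to the validity of the study.

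**What to change.** In the SAP for Parts A and B:

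1. In 6.3.2.1, delete the words restricting each-injection analyses to Part A, and state that the Placebo - mRNA-1273 group is summarized by first, second and any injection, including the headline percentages with exact confidence intervals.
2. In 5.2, define First and Second Injection Solicited Safety Sets for the Part B crossover group, mirroring Part A, and use them as denominators.
3. If the restriction is intended, list it in Section 7 with a reason and limit the later by-injection sentences to Part A.

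The cost is a short wording change and a few more tables. The eDiary is already activated and reviewed after each crossover dose, so no new data are needed. Version 5.0 of this SAP changes Part B only, and SAP 6.6.5 describes the final Part B analysis as still to come.

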6.3.2.2. Compliance of eDiary

Solicited ARs will be recorded in an eDiary on the day of each vaccine administration and for the 6 days after the day of injection. The completion status of the eDiaries among the 7-day period and on each individual day will be summarized.

6.3.3. Clinical Laboratory Evaluations

Safety laboratory testing will be performed in Part A of the study and will include hematology, serum chemistry, coagulation, and pregnancy test.

A pregnancy test will be performed on all female subjects of childbearing potential at the Screening Visit and before each vaccine administration (Day 1 and Day 29) via point-of-care urine, and as needed at unscheduled visits (urine or serum pregnancy test based on the Investigator's discretion).

All laboratory test results, including screening safety laboratory tests for Cohort 1 and Cohort 2 subjects and post-baseline tests for Cohort 2 subjects, will be presented in the data listings. The results that are outside the reference ranges will be flagged in the data listings. The abnormalities meeting the toxicity grading criteria in any safety laboratory (hematology, serum chemistry and coagulation) will be listed separately. If a subject has an

abnormal laboratory test at any post injection visit, then all results for that subject and laboratory test will be presented in the listing.

For continuous hematology, serum chemistry, and coagulation measurements, the observed values and changes from baseline will be summarized at each visit by vaccination group as defined in [Section 6.1](#) for Cohort 2. The number and percentage who had any abnormal result based on toxicity grades in hematology, serum chemistry, or coagulation measurements will also be summarized by visit and vaccination group for Cohort 2. Shift from baseline in the toxicity grades to the worst post-baseline result in the vaccination stage will also be summarized by vaccination group for Cohort 2.

6.3.4. Vital Sign Measurements

Vital sign measurements, including systolic and diastolic blood pressures, heart rate, respiratory rate, and body temperature, will be presented in a data listing. The values meeting the toxicity grading criteria will be flagged in the data listing. The abnormalities meeting the toxicity grading criteria (Grade 2 or higher) in any vital sign measurement will be listed separately. If a subject has a vital sign result with Grade 2 or higher abnormality at any post injection visit, then all results of vital sign measurement for that subject will be presented in the listing.

Observed values and changes from baseline for all vital sign measurements will be summarized at each visit by age cohort and vaccination group as defined in [Section 6.1](#) for Part A and Part B separately. Shift from baseline in the toxicity grades at each visit and shift from baseline in the toxicity grades to the worst post-baseline result will also be summarized by age cohort and vaccination group for Part A and Part B separately.

6.4. Immunogenicity Analysis

The analyses of immunogenicity will be based on the PP Set and will be performed by vaccination group as defined in [Section 6.1](#) for each age cohort, and for Part A and Part B separately, as applicable. If the number of participants in the FAS and PP Set differ (defined as the difference divided by the total number of participants in the PP Set) by more than 10% (for each age cohort), supportive analyses of immunogenicity may be conducted using the FAS. The supportive analysis is required if the condition is met.

The GMT and geometric mean (GM) level will be calculated using the following formula:

$$10^{\left\{ \frac{\sum_{k=1}^n \log_{10}(t_k)}{n} \right\}}$$

where t_1, t_2, \dots, t_n are n observed immunogenicity titers or levels.

The geometric mean fold-rise (GMFR) measures the changes in immunogenicity titers or levels within subjects. The GMFR will be calculated using the following formula:

$$10^{\left\{ \frac{\sum_{i=1}^n \log_{10} \left(\frac{v_{ij}}{v_{ik}} \right)}{n} \right\}} = 10^{\left\{ \frac{\sum_{i=1}^n \log_{10}(v_{ij}) - \log_{10}(v_{ik})}{n} \right\}}$$

where, for n subjects, v_{ij} and v_{ik} are observed immunogenicity titers or levels for subject i at time points j and k , $j \neq k$.

Seroresponse

Seroresponse in nAb or bAb at a participant level is defined as a change of nAb or bAb titer from below the LLOQ to $4 \times$ LLOQ or higher if the titer at baseline is $<$ LLOQ, or at least a 4-fold rise of titer if the titer at baseline is \geq LLOQ.

In addition to the above standard definition, there are assay specific definitions for seroresponse based on assay specific thresholds, as listed in [Table 3](#).

Table 3 Assay Specific Seroresponse

Category	Test Name	Definition Seroresponse
nAb	Pseudovirus Neutralizing Antibody ID50 Titers	baseline $<$ LLOQ: \geq LLOQ baseline \geq LLOQ: 3.3-fold-rise
	Pseudovirus Neutralizing Antibody ID80 Titers	baseline $<$ LLOQ: \geq LLOQ baseline \geq LLOQ: 2.3-fold-rise
bAb (ELISA)	VAC65 Spike IgG Antibody	baseline $<$ LLOQ: \geq LLOQ baseline \geq LLOQ: 4.6-fold-rise

bAb (Meso scale discoveries [MSD] MULTIPLEX)	SARSCOV2SP	baseline <LLOQ: >=LLOQ baseline >=LLOQ: 1.9- fold-rise
	All other tests	baseline <LLOQ: >=LLOQ baseline >=LLOQ: 4- fold-rise (unless specified otherwise)

For Part A, analyses for seroresponse were performed for selected assay tests based on assay specific definition for seroresponse.

For Part B booster subjects, seroresponse will be derived based on both the standard definition and assay specific definitions for seroresponse. The analyses will be performed using the titer value at pre-Dose 1 of primary series as the baseline and using the OL-D1 pre-booster titer as the baseline, respectively.

For Part B crossover subjects, seroresponse will be derived based on both the standard definition and assay specific definitions for seroresponse, using the titer value at OL-D1 as the baseline.

